### 1.5 Mesenchymal Stromal Cells (MSCs) as Therapy for Acute GVHD

[REDACTED]

MSCs have been shown to attenuate inflammatory and immunological processes relevant to GVHD. MSCs demonstrate immunosuppressive activity in T cell-driven immune responses in animal models of allogeneic skin graft rejection and GVHD. *In vitro*, MSCs suppress T-cell proliferation in response to allo-antigenic and mitogenic stimulation, and stimulate an increase in the regulatory T cell (Treg) population. Data suggest that Tregs play an important role in inhibiting allogeneic T cell response and aGVHD. In co-culture systems, MSCs alter the cytokine secretion profile of immune cells (dendritic cells, naïve and effector T cells, natural killer cells), decreasing expression of pro-inflammatory cytokines (e.g. IFN $\gamma$ , TNF $\alpha$ ) and increasing secretion of anti-inflammatory cytokines (e.g. IL-4, IL-10). The immunomodulatory effects of MSCs are attributable, at least in part, to secretion of soluble factors such as PGE2. In addition, MSCs may mediate tissue protection and repair at sites of injury in GVHD by secretion of soluble factors that are known to mediate processes such as inhibition of apoptotic cell death, recruitment of endogenous stem cell populations and angiogenesis.

[REDACTED]

### 1.8 Clinical Safety of Remestemcel-L

Refer to the remestemcel-L clinical safety as summarized in the MSB-GVHD001 protocol.

### 1.9 Potential Risks of MSCs

A list of adverse events (AEs) possibly or probably related to remestemcel-L use is found in the Investigator’s Brochure (IB) and in Protocol MSB-GVHD001 Section 1.7.8. All AEs were events commonly expected in the treated population, independent of the infusions of hMSCs. The most common adverse events observed for remestemcel-L in clinical trials of pediatric GVHD were infections, gastrointestinal disorders, and respiratory, thoracic and mediastinal disorders.

Due to the known immune modulating effects of hMSCs, there is a risk of immune suppression and increased infection risk. Subjects undergoing treatment for GVHD are typically severely immunocompromised. Treatment with remestemcel-L may lead to further immunosuppression. Therefore, the potential exists for an increased risk of infectious complications. Careful subject monitoring and appropriate anti-infective prophylaxis is recommended.

[REDACTED]

In theory, cells grown and expanded outside the body have the potential to be contaminated, and infection could be introduced to the subject at the time of infusion. This risk is made negligible by processing cells in a Good Manufacturing Practice (GMP)-compliant production facility, utilizing a closed system, and then by reconstituting them in a cell processing facility immediately prior to administration. The potential risks of introducing a donor-derived

infectious agent are minimized by strict adherence to the 21CFR1271 Subpart C Donor Eligibility and multiple screenings/testing of remestemcel-L for adventitious agents prior to release. The IB contains a full list of donor screening tests performed on all lots of remestemcel-L during production.

[REDACTED]

There has been no experience with pregnant women receiving infusions of remestemcel-L. The effects of remestemcel-L infusion on the developing fetus have not been established pre-clinically or in clinical trials. Thus, all females of childbearing potential (subjects  $\geq 10$  years of age) and post-pubescent males with female partners of childbearing potential are to consent to use an effective method of birth control during this treatment protocol in a manner that minimizes risk of failure. Abstinence is an option. Guidelines on childbearing potential and contraceptives are located in [Appendix 7](#).

### 1.10 Benefits

[REDACTED]

[Redacted]

[Redacted]

[Redacted]

[Redacted]

[Redacted]

[REDACTED]

## 2. CLINICAL RATIONALE

### 2.1 Rationale for the Study

There are currently no approved therapies for aGVHD in the US. Standard front-line treatment generally consists of corticosteroid, which produce a complete response in about half of all subjects. Even with the availability of corticosteroids, approximately 10% to 30% of aGVHD subjects develop more severe aGVHD of Glucksberg Grades III or IV. A variety of immunosuppressants are currently used as second-line therapy, though none of these have established efficacy against steroid-refractory aGVHD. The reported one-year survival rate for subjects that do not respond to steroid therapy ranges from 5% to 30%. There is thus a strong need for agents with demonstrated efficacy for treating steroid-refractory aGVHD.

MSB-GVHD001 will provide a series of prescribed doses of remestemcel-L and a follow up period of 100 days. There is a great interest in collecting data regarding treatment of aGVHD with respect to the duration of response, the ability to taper steroid and other secondary treatment and thereby mitigate potential side effects, the development of chronic GVHD after at least partial response to treatment, and any change in quality of life. Accordingly, this study will assess the efficacy and safety of remestemcel-L in pediatric patients with aGVHD refractory to corticosteroid.

### 2.2 Rationale for Study Design

Overall response, as defined by the response to treatment at Day 28, has been positively associated with non-relapse mortality at 6 months and 2 years. Response at Day 28 has been supported guidelines issued by the expert panel of the American Society for Blood and Marrow Transplant (ASBMT) in 2009 as well as by subsequent studies. Treatment of acute GVHD, which results in response by 28 days, has been shown to correlate well with survival rates at Day

100. Recovery after acute treatment as well as the period after treatment has been associated with an increased incidence of opportunistic infections and many other AEs, some due to the effects of the disease itself and many due to the treatment intervention, particularly with protracted high-dose steroid use. This study will provide safety data through 180 days after treatment of aGVHD. In addition, the present study will also provide information with regard to survival at Day 180, the ability to taper steroid doses and secondary medications and thereby mitigate potential risks, the development of chronic GVHD after at least partial response to treatment, quality of life (QoL), and duration of response. Though validated tools for QoL are limited for pediatric subjects, this study will evaluate several tools and accommodate those subjects too young to answer for themselves.

### **2.3 Rationale for Subject Population**

This study will explore duration of response and evaluate the safety of remestemcel-L in pediatric subjects with aGVHD that has failed to respond to first-line systemic steroid treatment who participated in MSB-GVHD001. The safety population will be comprised of any subject who received at least one infusion of remestemcel-L in MSB-GVHD001. Survival at Day 180 will be evaluated. Additionally, duration of response will be explored in subjects who completed initial therapy of remestemcel-L (first 8 doses) in MSB-GVHD001 and responded to therapy, in order to best assess the impact of a response to treatment of aGVHD.

### **2.4 Rationale for Dosing Regimen and Treatment Period**

There is no treatment intervention in this study; all remestemcel-L dosing will have occurred in the MSB-GVHD001 study.

## **3. STUDY OBJECTIVES**

### **3.1 Objectives**

In clinical studies, MSCs elicited improved clinical response over placebo in subjects with aGVHD, which will have been evaluated in the MSB-GVHD001 study. Here in protocol MSB-GVHD002, we will describe safety for the MSB-GVHD001 population through 180 days of remestemcel-L treatment and explore duration of response of treating aGvHD that has failed to respond to first-line steroid treatment in pediatric subjects.

### 3.2 Primary Objective

Safety through 180 days of remestemcel-L treatment in subjects who participated in Protocol MSB-GVHD001. No additional investigational agent (remestemcel-L) will be administered in this safety follow-up protocol.

### 3.3 Secondary Objectives:

1. To assess survival at 180 days
2. To obtain an assessment for GVHD activity to investigational medicinal product (IMP) administered in MSB-GVHD001.
3. To assess proportion of subjects able to taper steroids by 50% at each time point from Day 100 to Day 180.
4. To assess the time to addition of any second-line GVHD treatment agent
5. To assess the number of days to a GVHD flare
6. To evaluate subjects for evidence of chronic GVHD.

■ [REDACTED]

■ [REDACTED]

■ [REDACTED]

■ [REDACTED]

■ [REDACTED]

■ [REDACTED]

■ [REDACTED]

## 4. STUDY DESIGN

### 4.1 Overview of Study Design

This is a 180-day safety follow-up study of MSB-GVHD001, which will also explore duration of response over time. Subjects who participated in MSB-GVHD001 and received at least one remestemcel-L infusion will be evaluated at baseline (Day 100) and at Days 120, 140, 160 and 180 for safety endpoints. Subjects who participated in Protocol MSB-GVHD001 and received the first 8 doses of remestemcel-L, as outlined in that protocol, and showed overall response or VGPR at Day 28 will be evaluated at baseline (Day 100) and at Days 120, 140, 160 and 180 after initial remestemcel-L infusion for evidence of duration of response over time.

#### 4.1.1 Primary Endpoints

To describe the safety through 180 days of remestemcel-L treatment in subjects who participated in Protocol MSB-GVHD001 and received at least one infusion of remestemcel-L.

Safety parameters to be assessed include:

1. Adverse events
2. Serious adverse events
3. Survival through Day 180
4. Ectopic tissue formation.

#### 4.1.2 Secondary Endpoints

1. Survival at 180 days for subjects who received the complete initial therapy through 28 days as outlined in Protocol MSB-GVHD001
2. GVHD activity at time points evenly divided amongst the term from Day 100 to Day 180, specifically at Days 120, 140, 160 and 180, relative to baseline assessment in MSB-GVHD001.
3. Steroid doses at Days 120, 140, 160 and 180, including proportion of subjects able to taper steroids by 50% by each time point. Guideline for steroid taper is located in [Appendix 6](#).
4. Time to addition of any second-line GVHD treatment agent
5. The number of days to GVHD flares
6. Evidence of chronic GVHD at any time from Day 0 to Day 180. Guidelines for chronic GVHD assessment are located in [Appendix 8](#).

[REDACTED]

## 4.2 Study Duration

In the present study, MSB-GVHD002, subjects who participated in Protocol MSB-GVHD001 will be followed-up for safety and for duration of response from Day 100 through 180 days from MSB-GVHD001 Day 0. Subjects will be assessed in the present study according to the schedule of planned assessments, as summarized in [Table 6](#). Thus, the total duration of study participation per subject for Protocol MSB-GVHD001 and Protocol MSB-GVHD002 will be up to 180 days ( $\pm 7$  days), with the last 80 of the 180 days under Protocol MSB-GVHD002.

**Table 6: Schedule of Assessments and Procedures**

	Baseline/ Visit 1	Visit 2	Visit	Visit 4	Visit 5	
Study Days	Day 100 (same as Day 100 in MSB-GVHD001)	Day 120	Day 140	Day 160	End of Study/ Day 180	
Visit window	±7 days	±5 days	±5 days	±5 days	±7 days	Unscheduled
Inclusion/exclusion criteria/informed consent a	X					
Vital signs (HR, BP, Temp, RR, oxygen saturation) b		X	X	X	X	X
Height and weight					X	X
Physical examination		X	X	X	X	X
CMV c		X	X	X	X	X
Hematology laboratory tests				X	X	X
Chemistry laboratory tests				X	X	X
Urinalysis				X	X	X
Hospitalization d						X
Acute GVHD assessment (Skin, Lower GI, Upper GI, Liver)						
Acute GVHD assessment (Skin, Lower GI, Upper GI, Liver)		X	X	X	X	X
Chronic GVHD assessment						
Chronic GVHD assessment		X	X	X	X	X
Concomitant medicationf						
Concomitant medication f		X	X	X	X	X
Transfusiong						
Transfusion g						X
Optional CT scan or MRI (Chest, Abdomen and Pelvis)l						
Optional CT scan or MRI (Chest, Abdomen and Pelvis) l					X	X
12-Lead ECG						
12-Lead ECG					X	X
Termination/end of study						
Termination/end of study					X	X
Pregnancy testl						
Pregnancy test l					X	X
Adverse event evaluationk						
Adverse event evaluation k		X	X	X	X	X

a Informed consent for MSB-GVHD002 may be provided to the subject simultaneously with the informed consent for MSB-GVHD001, or at any visit prior to Day 180 (± 7 days) .

b Vital signs include measurements of heart rate (HR), blood pressure (BP), respiratory rate (RR), and temperature (temp).

c Investigators should provide standard of care treatment for viral infections as appropriate, including prophylaxis and treatment if there is evidence of viral reactivation and/or infection

d Hospitalization with a start date after the visit window of Day 100 (Day 107) will be collected in MSB-GVDH002.

Hospitalization with a start date before the visit window of Day 100 (Day 106) will be collected in MSB-GVDH001.

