### Analysis Populations

The analysis population for the safety assessment in this study will include all subjects from Protocol MSB-GVHD001 who have signed the Informed Consent form and have received at least one dose of remestemcel-L. The analysis population for the duration of response assessments in this study will include Protocol MSB-GVHD001 subjects with overall response and VGPR to remestemcel-L at Day 28, who have signed the Informed Consent form and have completed treatment for the first 28 days, as prescribed in Protocol MSB-GVHD001.

[figure not shown]

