### 5.2 Eligibility Criteria

#### 5.2.1 Inclusion Criteria

Subjects are eligible for the study if all of the following criteria are met:

1. Subjects must have participated in Protocol MSB-GVHD001 and have received at least one infusion of remestemcel-L.
2. Subject or subject's authorized representative must provide written informed consent. Assent, if applicable, must also be collected when required by the IRB/EC.
3. Female subjects of childbearing potential ( $\geq 10$  years of age) ([Appendix 7](#)) must use a medically accepted method of contraception and must agree to continue use of this method for the duration of the study and for the follow-up time period. Acceptable methods of contraception include abstinence, barrier method with spermicide, intrauterine device (IUD), or steroidal contraceptive (oral, transdermal, implanted, and injected) in conjunction with a barrier method.
4. The subject must be willing and able to comply with study procedures, remain at the clinic as required during the study protocol, and return to the clinic for the follow-up evaluations as specified in this protocol.

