## 6. STUDY PROCEDURE

### 6.1 Visit Schedule and Assessments

Table 6 lists all planned assessments, which are marked with an “X” when the visits are performed. Subjects should be seen for all visits on the designated day or at a time that is as close as possible to the designated day. The study assessment schedule in Table 6 outlines all procedures to be performed on subjects at the scheduled visits.

In order to minimize variability in evaluations, ideally, the same individuals should perform the same tests on all the subjects at a given trial site.

The following assessments and procedures will be performed at study visits:

- Informed consent. Subject may be consented on MSB-GVHD002 simultaneously when being provided with the MSB-GVHD001 consent, or at any visit up through Day 180 ( $\pm$  7 days). If the IRB/EC has not yet approved the consent for MSB-GVHD002 at Day 100 (MSB-GVHD001), the Investigator should make all efforts to have the IRB/EC approved consent for MSB-GVHD002 presented to the subject no later than Day 180 ( $\pm$  7 days). See Section 6.3 for additional information about handling of visits from Day 100 through Day 160 when an IRB/EC approved consent is not available.
- Review of inclusion / exclusion criteria
- Physical examination
- Height and weight
- Vital signs (heart rate [HR], blood pressure [BP], temperature, and respiratory rate [RR])
- GVHD assessment (skin, lower GI, upper GI, liver) using the same method as that of MSB-GVHD001
- O2 saturation by pulse oximetry (SaO2/SAT)
- Adverse event (AE) assessment
- Incidence of chronic GVHD (cGVHD) (Appendix 8)
- Survival status
- Information on hospitalization status (namely the date of hospitalization)
- Steroid dose(s)
- Prior and concomitant medications

- Laboratory assessments
  - Hematology (including CMV, please see [Table 6](#) for details)
  - Serum chemistry
  - Urinalysis
- [REDACTED]
- Optional CT scan or MRI of the chest, abdomen, and pelvis at the discretion of the investigator. Scans may contribute information with regard to baseline disease burden and may also provide baseline for evaluation of future possible ectopic tissue formation. For CT, use intravenous (IV) contrast; if IV is contraindicated for any reason, oral is acceptable even in the presence of GI GVHD.
- 12-Lead ECG
- [REDACTED]
- [REDACTED]
- [REDACTED]

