## 6.3 Missing or Delayed Study Visits

Every effort should be made to ensure compliance with prescribed study visits. Missing of study visits is generally not permitted. However, in exceptional situations and with the sponsor's approval, visits may be postponed.

Subjects may be consented on MSB-GVHD002 simultaneously when being provided with the MSB-GVHD001 consent, or at any visit up through Day 180 ( $\pm 7$  days). Due to IRB/EC review times, there may be situations in which there is a delay in the IRB/EC approval for MSB-GVHD002 and the associated informed consent forms. If the IRB/EC approval for MSB-GVHD002 consent form is not available at Day 100, Day 120, Day 140, and/or Day 160, these visits will be marked as missed visits in EDC. Data collection for MSB-GVHD002 will begin once the subject has signed consent for MSB-GVHD002. The Investigator should make every effort to present the IRB/EC approved consent for MSB-GVHD002 to the subject no later than Day 180 ( $\pm 7$  days).

To ensure timely attendance at the required clinic visits, the visit schedule for the entire study period should be arranged and agreed upon with the subject at the baseline visit. The study site should document and notify the sponsor of any visits not completed within the specified time frame or within the allowable window period.

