### 9.2 Analysis Population

The analysis population for safety in this study, the Safety Population, will include all subjects who received at least one dose of the study treatment in study MSB-GVHD001 and entered into study MSB-GVHD002. The population to be evaluated for duration of response will include all subjects who participated in Protocol MSB-GVHD001, received the first 8 doses of remestemcel-L as outlined in that protocol, and showed overall response (OR) or very good partial response (VGPR) to remestemcel-L at Day 28.

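### Table 6 and Sections 6.1/6.3 disagree on whether MSB-GVHD002 consent may first be given at the Day 180 visit, and under any late consent the entered population gains only survivors with little observed extension time

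*Combined protocol and SAP*

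**What the plan says.** Table 6, footnote a, allows MSB-GVHD002 consent together with the MSB-GVHD001 consent "or at any visit prior to Day 180 (± 7 days". Sections 6.1 and 6.3 each allow it "or at any visit up through Day 180", with the same 7-day window. Section 6.1 adds that, where ethics approval is late, the approved form should be "presented to the subject no later than Day 180", and Section 6.3 repeats that limit.

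Section 6.3 foresees approval being unavailable at Days 100, 120, 140 and/or 160. In that case "these visits will be marked as missed visits in EDC". It then says: "Data collection for MSB-GVHD002 will begin once the subject has signed consent for MSB-GVHD002". Sections 7.1.1 and 9.4.1 likewise start adverse event collection when the consent form is signed.

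Consent also decides who is analysed. Inclusion criterion 2 in Section 5.2.1 reads "Subject or subject's authorized representative must provide written informed consent". The synopsis (Analysis Populations) limits the safety analysis to MSB-GVHD001 subjects "who have signed the Informed Consent form and have received at least one dose of remestemcel-L". Section 9.2 requires a dose in MSB-GVHD001 and that the subject "entered into study MSB-GVHD002". Survival through Day 180 is one of the primary safety parameters in Section 4.1.1.

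**The concern.** Read plainly, footnote a stops at the visit before Day 180, while the two body sections include the Day 180 visit. A child whose first chance to consent is that visit falls inside one wording and outside the other, and no passage says which governs. The case is not far-fetched: Section 6.3 provides for it when ethics review is slow.

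Settling the wording leaves a second problem. Entry is conditional on being alive to consent. If two children at a site wait for approval and one dies at Day 150, only the other can enter. The entered population therefore gains survivors and not the matching deaths. The late entrant also counts fully in the adverse event denominator, with almost none of the extension period under observation. Both effects bear on the study's primary safety description and flatter it in the same direction.

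**Working it through.** The documents give no sample size, expected survival rate or number of late consenters for this point, so there is no figure to reproduce. The check is a comparison of passages followed by an illustration under stated assumptions.

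**Comparison, for a child first offered consent at the Day 180 visit**

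- Table 6, footnote a: outside the wording, since it refers to visits before Day 180.
- Sections 6.1 and 6.3: inside the wording, and the form may still be presented then.
- Section 5.2: eligible if written consent is given; no study-day limit.
- Section 9.2 and synopsis, Analysis Populations: in the safety population once consented and entered.
- Visit window in Table 6: 180 − 7 = 173 to 180 + 7 = 187. The child is known to be alive at that visit, which can fall up to 7 days before Day 180.

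**Survival in the entered population (assumed inputs)**

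Let s be true survival from Day 100 to Day 180. Let f be the share of children alive at Day 100 whose first chance to consent is the Day 180 visit. Assume that late and timely children have the same s and that everyone offered consent accepts.

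- Late group left out: apparent survival = s.
- Late group admitted at Day 180: all timely children count, but only the late survivors do. Apparent survival = s / [s + (1 − f)(1 − s)].

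With s = 0.80:

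- f = 0.10: 0.80 / (0.80 + 0.90 × 0.20) = 0.80 / 0.98 = 81.6%
- f = 0.20: 0.80 / (0.80 + 0.80 × 0.20) = 0.80 / 0.96 = 83.3%
- f = 0.50: 0.80 / (0.80 + 0.50 × 0.20) = 0.80 / 0.90 = 88.9%

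Over s from 0.70 to 0.90 and f from 0.05 to 0.50, the excess over s runs from 0.5 points (s = 0.90, f = 0.05: 0.90 / 0.995 = 90.5%) to 12.4 points (s = 0.70, f = 0.50: 0.70 / 0.85 = 82.4%).

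In counts, take an assumed 50 children alive at Day 100, with s = 0.80 and f = 0.20. There are 40 timely children, of whom 32 survive, and 10 late children, of whom 8 survive. Without the late group, survival is 32/40 = 80.0%. With it, survival is (32 + 8)/(40 + 8) = 40/48 = 83.3%. All 8 added children are survivors, and the 2 late deaths are never seen.

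**Adverse event incidence, same counts**

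If the 8 late entrants contribute no observed extension-period event (the limiting case), any incidence proportion among the 40 is multiplied by 40/48 = 0.833.

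**What entry at the consent date does**

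If late children join the risk set only from their consent date, those entering at the Day 180 visit add no time before it. The estimate then rests on the 40 children followed throughout, 32/40 = 80.0%, which equals the assumed s. This needs the timing of consent to be unrelated to prognosis. That is plausible when the cause is ethics review time, but it remains an assumption.

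**The case against.** Several points on the other side are sound.

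- **Eligibility.** A reader might infer that Table 6 makes a first consent at Day 180 ineligible. It does not go that far. Footnote a is permissive, Section 5.2 sets no day limit, and Section 5.1 enrols every MSB-GVHD001 subject who meets the criteria.
- **Intended rule.** Section 4.2 treats Table 6 as a summary, Section 6.1 sends the reader to Section 6.3 for late approval, and both sections state the window and the deadline consistently. Footnote a could even be read as meaning before the window closes at Day 187, though a reference to visits before Day 180 does not naturally say that.
- **Site practice.** A reader might infer that inclusion will vary across the roughly 40 sites. Nothing in the documents shows that sites would apply different rules.
- **Denominator.** Section 9.1 presents survival over both trials, Section 9.4.2 summarises disposition from Day 0 of MSB-GVHD001, and Section 9.5.1 bases the responder-by-survivor percentages on all subjects, including those with missing survival. If that means every treated MSB-GVHD001 child, those who never entered would appear as missing and the percentages above would not apply. The synopsis paragraph on study population also describes the safety population without consent or entry.
- **Retrospective capture.** Footnote k assigns adverse events by onset date, so earlier events might be recorded after a late consent. Sections 6.3, 7.1.1 and 9.4.1, however, all tie collection to consent.

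What remains is the wording conflict and, for any analysis in the entered population of Section 9.2, the survivor-only entry and short observation of late consenters.

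**Conclusion.** The concern holds, as a minor point. Footnote a and Sections 6.1 and 6.3 conflict in current text and must be reconciled; the body text indicates consent up through the Day 180 visit. In the population defined by Section 9.2 and the synopsis, late consent biases survival upward and extension-period adverse event incidence downward whenever some children consent late and some die while waiting.

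The direction follows from the rules; the size does not. The range of 0.5 to 12.4 points rests on assumed s and f, equal survival in late and timely children, and a denominator of entered children. It should not be read as an estimate for this trial.

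A reader might also infer that correcting the footnote removes the bias. It does not, because a first consent at Day 120, 140 or 160 equally requires survival to that visit. The Day 180 visit is only the extreme case.

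**What to change.** 1. Align Table 6, footnote a, with Sections 6.1 and 6.3, so that consent is allowed up to and including the Day 180 visit.
2. Record the study day of MSB-GVHD002 consent for every child and derive a flag for first consent at the Day 180 visit.
3. Keep all entered children in the Safety Population, the listings and the Day 180 assessments, so that Section 9.2 and the synopsis need no change on this account. Alongside the full result, report extension-period adverse event incidence without the flagged children.
4. For Day 180 survival in the entered population, let late consenters join the risk set at their consent date, or add a sensitivity analysis limited to children consented by Day 100. State in the SAP which is used and which survival tables use entered children rather than all treated MSB-GVHD001 subjects.

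The cost is a footnote edit, one recorded date with one derived variable, and one extra analysis. Denominators in the restricted results become slightly smaller and their confidence intervals slightly wider. No treatment or assessment changes.
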